6.3.12.4 Time Invariance (Part B Only)

If data permits, the time invariance ratio will be calculated as the ratio of AUC(0- τ) on Day 7 to AUC(0- ∞) on Day 1 (If have reliable AUC(0- ∞) on Day 1) for each subject in each cohort. An ANOVA with terms for subject as a random effect and day as a fixed effect will be performed by dose on the loge-transformed AUC. Day will be treated as a class variable in the model. The time invariance of KM-819 will be assessed by calculating the ratio of the geometric least square means of AUC(0- τ) to AUC(0- ∞) and the corresponding 90% CI for each dose. AUC(0- ∞) on Day 1 will be considered as the reference phase in the analysis [Table 14.2.5].

An example of SAS code is included here.

ODS output solutionf=stat;

Proc Mixed;

by dose;

class subject day;

model logAUC = day / ddfm=kr;

random subject;

lsmeans day;

estimate 'test vs ref' day -1 1/cl alpha=0.1;

run;

The time invariance ratio will also be listed and summarized along with other PK parameters.

6.3.12.5 Steady State Assessment (Part B Only)

To evaluate whether steady state was achieved, statistical analysis of $C\tau$ levels will be performed before Day 7, after a log-e transformation of the data from all active treatment doses. Only pre-dose concentration on days 1-7 for the 7 day analysis will be included in the analysis. A mixed effect model

Kainos Medicine, Inc.

Final 1.0

KMCP-819-K101

14/Nov/2017

TP-EP.BS-WW-001-05

Effective date: 29 Jul 15

Related to: SOP-EP.BS-WW-002

Page 41 of 61

PAREXEL International

Statistical Analysis Plan

will be fitted separately with day as a continuous covariate and subject as a random effect. The coefficient of the slope of the day effect on the log-e scale for each treatment dose will be used to assess whether steady state was achieved on Day 7. Using the estimate of variance, the 90% confidence intervals for the slopes will be calculated. If the 90% limits for the slope is including one then steady-state is statistically confirmed.[Table 14.2.6].

An example of SAS code to assess achievement of steady-state is included here.

```
ODS output solutionf=stat;  
Proc Mixed;  
  by dose;  
  where (Day in (1,2,3,4,5,6,7));  
  class subject;  
  model logCtau = Day/cl alpha=0.1 solution;  
  random intercept/subject=subject type=un;  
run;
```

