### **5.3 Rationale for Selection of Starting Dose**

The FDA Guidance “Estimating the Safe Starting Dose in Clinical Trials for Therapeutics in Adult Healthy Volunteers” and allometric scaling modeling and simulation were used for the initial calculation of the starting human dose in this study. Based on the FDA Guidance document and the 4-week rat toxicology study NOAEL of 500 mg/kg/day, the human equivalent dose (HED) is estimated to be 5600 mg for a 70 kg human subject. A 10-fold safety factor is applied to the HED, resulting in an estimated Maximum Recommended Starting Dose (MRSD) was 560 mg per person for a 70 kg person. In addition to the FDA Guidance method, an allometric scaling method was used to predict human PK. The human PK parameters were predicted as followed: CL= 2.93 L/h, V = 39.2 L, and half-life =9.27 hours. Using these predicted human PK parameters, simulation was conducted based on the assumption that human PK behaves with one compartment model with first order absorption and first order elimination rate and the bioavailability was assumed to be 35% (mean F from animal data).

Based on simulated human PK profile and animal efficacy data, a lower dose was chosen for the starting dose.

The first-in-human Phase 1 single ascending dose study will have an initial starting dose of 10 mg, which is x56-fold below the estimated MRSD derived from the rat NOAEL.

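### The steady-state check fits one straight line through build-up and plateau troughs, so with the null set at 0 it reports 'not achieved' too often when accumulation is material

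*SAP*

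**What the plan says.** SAP 6.3.12.5 gives the data, the model, the purpose and the decision rule.

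- **Data:** "Only pre-dose concentration on days 1-7 for the 7 day analysis will be included in the analysis". The sample code agrees: "where (Day in (1,2,3,4,5,6,7". The section's opening sentence speaks of troughs before Day 7, but the next sentence and the code both include Days 1 to 7.
- **Model:** a mixed model "will be fitted separately with day as a continuous covariate and subject as a random effect", coded as "model logCtau = Day/cl alpha=0.1 solution" with a random intercept per subject, run separately by dose.
- **Purpose:** the day slope "for each treatment dose will be used to assess whether steady state was achieved on Day 7".
- **Rule:** "If the 90% limits for the slope is including one then steady-state is statistically confirmed".

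Nothing else in the SAP or protocol drops the early troughs, compares successive days or contrasts a day with later days. Protocol 8.7 does not describe a steady-state test. Protocol Table 7-4 shows pre-dose samples on Days 1 to 7 and a 24 h sample after the last dose, on Day 8. The steady-state analysis does not use the Day 8 sample.

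**The concern.** Steady state on Day 7 concerns the end of the trough profile, whereas a single line over the whole week averages the rise and the plateau. If the first one or two troughs are clearly below plateau, the expected slope is positive however flat the later troughs are. The verdict then depends largely on the accumulation ratio and the residual noise.

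At stake is Table 14.2.6, which applies a prespecified rule to each dose. Multiple-dose PK is a secondary objective, and Protocol 1.3 says the data will guide dosing in later studies. A table reporting that steady state was not reached, for a drug flat from Day 4, would also confuse the reading of Day 7 AUCtau and the accumulation ratios.

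**Working it through.** **Inputs from the documents.** Protocol 5.3 gives CL 2.93 L/h, V 39.2 L, "half-life =9.27 hours" and one compartment with first-order absorption and elimination. Dosing is once daily for 7 days, with 6 active subjects per cohort. Protocol 1.2.1.3 gives oral half-lives of 6.06 h in rats and 4.96-5.03 h in dogs.

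**Assumptions.** The within-subject SD of log trough is not in the documents; 0.10 to 0.40 was tried. Absorption is taken as complete by 24 h. Human half-lives other than 9.27 h are sensitivity values.

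**Plan's own figure.** Half-life = ln2 × 39.2 / 2.93 = 9.27 h, which reproduces.

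**Day 1.** The sample precedes any drug. SAP 6.1.3.1 sets non-quantifiable values before the first measurable one to zero, and the log of zero is undefined, so the record drops out and the fit is Days 2-7. If a small positive value were substituted (0.1% to 5% of the plateau trough, assumed), the expected slope at 9.27 h would be 0.75 to 0.33 per day.

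**Troughs.** The fraction of plateau on day d is 1 − r^(d−1), with r = exp(−24 ln2 / 9.27) = 0.166. Days 2 to 7 are 83.4, 97.2, 99.5, 99.9, 100 and 100%. The accumulation ratio is 1/(1 − 0.166) = 1.20.

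**Expected slope.** With day centred (−2.5 to 2.5), Sxx = 17.5. The sum of centred day × log fraction is 0.454 (Day 2) + 0.042 (Day 3) + 0.002 (Days 4-7 together) = 0.498. The slope is 0.498 / 17.5 = 0.0285 per day. Day 2 alone supplies 0.454 / 0.498 = 91% of it. For Days 5-7 the expected slope is 0.0004.

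**How often the 90% CI excludes 0.** At least 20,000 simulated cohorts per cell, n = 6, random subject intercept, 29 df for Days 2-7. A valid check gives 10%.

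| Half-life | Day 7 trough, % of plateau | SD 0.15 | SD 0.20 | SD 0.30 |
|---|---|---|---|---|
| 5 h | 100 | 12% | 11% | 11% |
| 6 h | 100 | 17% | 14% | 12% |
| 9.27 h (protocol) | 100 | 57% | 39% | 24% |
| 12 h (assumed) | 100 | 90% | 72% | 45% |
| 16 h (assumed) | 99.8 | over 99% | 97% | 76% |

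At 9.27 h the rate is 84% at SD 0.10 and 18% at SD 0.40. With Days 5-7 only it is about 10% at 9.27 h for every SD tried.

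**Does adding Day 8 alone cure it?** No. Days 2-8 at SD 0.20 still gives about 38% at 9.27 h and 70% at 12 h.

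**Price of a late window.** The approximate CI half-width is t × SD / √(6 Sxx). At SD 0.20:
- Days 2-7: 1.699 × 0.20 / √105 = 0.03 per day
- Days 5-7: 1.796 × 0.20 / √12 = 0.10 per day
- Days 5-8: 1.740 × 0.20 / √30 = 0.06 per day

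At an assumed 48 h half-life the Day 7 trough is only 87.5% of plateau. At SD 0.20, Days 5-7 excludes 0 in about 35% of cohorts and Days 5-8 in about 52%. Days 2-7 does so in essentially all.

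**The case against.** Several objections stand and limit the point.

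- **The effect is masked as written.** The slope is on the log scale, where no trend is 0, but the rule asks whether the interval includes one. Taken literally, no simulated cohort met it, even at exact steady state. Pooling the early troughs changes a conclusion only after that null is corrected, so both belong in one rewrite of the section.
- **The size rests on assumptions.** No human SD or observed half-life is available. At the animal oral half-lives the error rate is near nominal, and half-lives of 12 h or more appear nowhere in the documents.
- **Little hangs on the table.** Steady state is not an objective or a listed endpoint. Escalation uses safety, tolerability and exposure, and nothing in the SAP is conditional on this result. Trough summaries, listings and plots would still show a plateau. With the null at 0 the error is in the cautious direction.
- **The remedy has its own weakness.** A three-trough slope in 6 subjects is imprecise, so it can miss a slow approach to plateau.

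None of these removes the mechanism, which is in both text and code. Correcting the null and adding Day 8 without dropping the early days leaves it in place.

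**Conclusion.** The point holds with bounded size. For a drug with material accumulation, a line over Days 2-7 is not a valid check of the state on Day 7. With the null at 0, it rejects about 57%, 39% or 24% of cohorts at the protocol's predicted half-life (assumed SD 0.15, 0.20 or 0.30), although the Day 4 trough is already 99.5% of plateau. The figures assume one-compartment build-up, 6 evaluable subjects and Day 1 dropping out.

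A reader might infer that the model simply tests whether the drug accumulated at all. The documents do not support that. At 9.27 h the drug does accumulate (ratio 1.20), yet the interval still covers 0 in about 60% of cohorts at SD 0.20 and 76% at SD 0.30. At 5 h (ratio 1.04) the check behaves almost nominally. Nor is every fitted slope positive; only its expectation is. A reader might also take the near-certain failures at 12-20 h as a forecast for KM-819, but those half-lives are assumptions. The section should be changed, but no other planned conclusion depends on it.

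**What to change.** Rewrite SAP 6.3.12.5 and its sample code together:

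1. Remove the Day 1 pre-dose value and the build-up troughs from the WHERE statement. Fit the slope to Days 5, 6 and 7 plus the 24 h sample on Day 8, which Protocol Table 7-4 already collects. Helmert-type contrasts of each day's log trough with the mean of later days are an alternative.
2. Set the null at 0 on the log scale, equivalently a ratio of 1 after exponentiation.
3. Report the per-day geometric ratio with its 90% CI for each dose.
4. Replace the wording that steady state is statistically confirmed. State that an interval covering the null is consistent with steady state and does not prove it. The same caution applies to the contrasts.

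The cost is SAP text and a few lines of code, with no new samples. The statistical price is precision: at SD 0.20 the half-width is about 0.06 per day for Days 5-8 (0.10 for Days 5-7), against 0.03 for Days 2-7. There is also less ability to detect a slow approach to plateau, about 52% (Days 5-8) or 35% (Days 5-7) at an assumed 48 h half-life. That is why the Day 8 sample and the reported interval are part of the fix.

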**Figure 3-1: Part A Single Ascending Dose Study Design**

**Part B, Multiple Ascending Dose (MAD)**

Part B will be conducted after completion of all cohorts of young adult male subjects in Part A. Up to 32 healthy young adult male subjects and 8 healthy elderly male or post-menopausal female subjects will be enrolled and randomized to receive either KM-819 or placebo.

Each of the 4 dose escalation cohorts will consist of 8 healthy young adult male subjects; 6 subjects will receive 30, 100, 200, or 400 mg of KM-819 once a day (QD) for 7 days and 2 subjects will receive placebo. Cohorts will be dosed sequentially with escalating doses.

After completion of the 4 dose escalation cohorts, 8 elderly male or post-menopausal female subjects will be enrolled into an additional cohort; 6 subjects will receive 200 mg KM-819 QD for 7 days and 2 subjects will receive placebo.

[figure not shown]
See Table 3-2 for Part B dose groups.

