6. Screening height and weight will be used for BMI calculation for assessment of eligibility.
7. Blood will be tested for HBsAg, anti-HAV IgM, anti-HCV Ab, and anti-HIV Ab.
8. All hematology and serum chemistry labs will be taken after fasting for a minimum of 8 hours.
9. Simple spine X-ray examination will only be conducted at Screening for healthy elderly cohort.
10. Plasma samples for pharmacokinetics of KM-819 will be obtained on Day 1 predose (within 30 minutes prior to study drug administration) and 0.25, 0.5, 1, 2, 4, 6, 8, and 12 hours postdose, predose on Days 2, 3, 4, 5, 6,

---

and on Day 7 predose (within 30 minutes prior to study drug administration) and 0.25, 0.5, 1, 2, 4, 6, 8, 12, and 24 hours postdose.

11. CSF samples for pharmacokinetic of KM-819 will be obtained on Day 1 (at -120 minutes to 0 minute prior to the first dosing) and on Day 7 (at 1 hour after last dosing).
12. CSF samples for pharmacodynamic of KM-819 will be obtained on Day 1 (at -120 minutes to 0 minute prior to the first dosing) and on Day 7 (at 1 hour after last dosing).
13. Plasma samples for pharmacodynamic of KM-819 will be obtained on Day 1 (within 30 minutes prior to study drug administration) and on Day 7 (at 1 hour after last dosing).
14. Bond and Lader VAS, POMS, and K-WAIS-IV will be performed on Day -1, on Day 1 and Day 7 at predose, 3, 6, 12, and 24 hours postdose ( $\pm$  30 minutes for each time point).
15. The version of the C-SSRS to be performed at Screening is the “Baseline-Screening for Phase 1,” and the version of the C-SSRS to be performed on Day 3 and Day 8 (or at ED) is the “Since Last Visit”.

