- vital signs measurement (predose)

- scales assessments (predose)
- PK blood sampling within 30 minutes before dosing

Study drug will be administered from 8:00 to 10:00.

The procedures to be performed at postdose are listed below:

- postdose PK blood sampling at 0.25, 0.5, 1, 2, 4, 6, 8, and 12 hours (see Table 7-2)
- Plasma PD sampling (at 1 hour postdose)
- CSF PK and PD sampling (at 1 hour postdose)
- postdose scales assessments at 3, 6, and 12 hours

The following assessments will be also performed during Day 7:

- concomitant medication
- assessment of AE

On Day 8, the procedures to be performed are listed below:

- concomitant medication
- assessment of AE
- vital signs measurement and physical examination
- ECG assessment
- hematology and biochemistry blood sampling
- urinalysis sampling
- PK blood sampling at 24 hour after last dosing
- scales assessments at 24 hours after last dosing
- C-SSRS assessment

Subjects will be allowed to leave the study center after completing all the procedures on Day 8.

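### The steady-state model omits the 24-hour sample after the last dose, although it is already collected: a nearly free improvement with a small effect

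*SAP*

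**What the plan says.** SAP 6.3.12.5 analyses log-transformed Ctau by dose, with day as a continuous covariate and subject as a random effect. On which samples enter, it says: "Only pre-dose concentration on days 1-7 for the 7 day analysis will be included in the analysis". The example code carries the same restriction, "where (Day in (1,2,3,4,5,6,7". The opening sentence of the paragraph says that the analysis of Ctau "levels will be performed before Day 7", which does not fit a filter that includes Day 7. The slope "will be used to assess whether steady state was achieved on Day 7", and a 90% confidence interval for the slope that includes one is taken as confirmation.

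The protocol samples beyond the Day 7 pre-dose time. Footnote 10 of Table 7-2 runs the Day 7 profile at "0.25, 0.5, 1, 2, 4, 6, 8, 12, and 24 hours postdose". The Day 8 list in section 7.2.3.1 has "PK blood sampling at 24 hour after last dosing", and Table 7-4 gives that sample a Day 8 row with a window of ±15 minutes. Part B dosing is once daily: "6 subjects will receive 30, 100, 200, or 400 mg of KM-819 once a day (QD) for 7 days". The SAP gives no reason for leaving the Day 8 sample out.

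**The concern.** With a 24-hour dosing interval, the Day 7 pre-dose sample closes the Day 6 interval, and the sample 24 hours after the last dose closes the Day 7 interval. The conclusion is about Day 7, yet the end-of-interval concentration for Day 7 is not in the model. Table 7-4 labels the Day 2 pre-dose sample as the 24-hour value after the first dose. The Day 8 sample is its counterpart after the last dose.

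The filter does keep the Day 1 pre-dose sample. This is a first-in-human study, so that sample should hold no drug. SAP 6.1.3.1 sets non-quantifiable values before the first measurable concentration to zero, and zero has no logarithm. In effect the model runs on Days 2-7. It retains the troughs where accumulation is still visible and drops the latest one available. What is at stake is the precision of the slope and how heavily early build-up weighs in it.

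**Working it through.** The documents state no power or precision for this analysis, so there is no design figure to reproduce. The one input that can be checked does reproduce: ln 2 × 39.2 / 2.93 = 9.27 h, the predicted half-life in protocol 5.3.

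**Inputs.** From the documents: six active subjects per cohort, a separate fit by dose, a 24-hour interval, seven doses, a 90% interval and a half-life of 9.27 h. Assumed, because the documents give no value: within-subject residual SD of log trough from 0.15 to 0.40; independent residuals around a random intercept; one-compartment accumulation; other half-lives of 24 and 48 h.

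**Precision.** The slope SE is σ / √(n·Sxx), where Sxx is the sum of squared deviations of day from its mean.
- Days 2-7: Sxx = 17.5 (36 points per cohort). Days 2-8: Sxx = 28 (42 points).
- SE ratio = √(17.5/28) = 0.79, a 21% reduction that does not depend on σ.
- The 90% half-width falls from 0.025 to 0.020 at SD 0.15, from 0.050 to 0.039 at SD 0.30, and from 0.066 to 0.052 at SD 0.40.

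**Trough as a fraction of steady state.** At pre-dose day d the fraction is 1 − exp(−24k(d−1)), with k = ln 2 / half-life.

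| Half-life | Day 2 | Day 4 | Day 7 | Day 8 |
|---|---|---|---|---|
| 9.27 h (predicted) | 83.4% | 99.5% | 99.998% | about 100% |
| 24 h (assumed) | 50.0% | 87.5% | 98.4% | 99.2% |
| 48 h (assumed) | 29.3% | 64.6% | 87.5% | 91.2% |

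**Effect on the verdict.** Adding Day 8 also shrinks the expected slope, because the slope over Days 2-7 is largely early build-up. The signal relative to its error is slope × √Sxx:
- 9.27 h: 0.0285 × √17.5 = 0.119 against 0.0216 × √28 = 0.114, a change of −4%.
- 24 h: 0.1207 × √17.5 = 0.505 against 0.0965 × √28 = 0.511, +1%.
- 48 h: 0.2033 × √17.5 = 0.851 against 0.1703 × √28 = 0.901, +6%.

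**Simulation.** Share of 90% intervals that cover zero (20,000 runs, six subjects):

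| Half-life, SD | Days 2-7 | Days 2-8 | Days 4-7 | Days 4-8 |
|---|---|---|---|---|
| 9.27 h, 0.20 | 60% | 63% | 90% | 90% |
| 9.27 h, 0.30 | 76% | 77% | 90% | 90% |
| 24 h, 0.30 | 1% | 1% | 83% | 81% |
| 48 h, 0.30 | 0% | 0% | 45% | 33% |

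At 9.27 h the rise from 60% to 90% comes from removing the early troughs, not from Day 8. Day 8 pays once the set is late: Sxx goes from 5 (Days 4-7) to 10 (Days 4-8), the SE falls by 1 − √(5/10) = 29%, and at 48 h a false plateau falls from 45% to 33%.

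**The written rule.** In these runs essentially no interval included one, at any half-life and with any set of days. Under the rule as written, neither set of samples would confirm a true plateau.

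**The case against.** The SAP's choice is coherent. Troughs up to the Day 7 dose can show whether a plateau existed when the profiled interval began. Protocol 3.2.2 defines Ctrough as the concentration before dosing, and no dose follows the Day 8 sample. The Day 8 value is not lost either: it closes the Day 7 AUCtau and is listed and summarised. At the only half-life the protocol predicts, Days 7 and 8 are both above 99.99% of steady state. All of this stands, and it is why the point is small.

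Two stronger readings are tempting. A reader might infer that AUCtau, the accumulation ratios and the time-invariance analysis depend on this test. The documents do not support that. SAP 6.1.3.1 computes AUCtau and the accumulation ratios directly from observed data. SAP 6.3.12.4 makes time invariance conditional only on the data permitting it and on a reliable Day 1 AUC to infinity. Interpreting these as steady-state quantities is helped by a sound test, but no section makes them conditional on it. A reader might also take the 21% as an improvement in the verdict. It is not, because the slope shrinks along with its error while Day 2 stays in.

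There is also a comparability point. Protocol 5.2 applies a 2-hour post-dose food rule on Days 2-6, while the general 4-hour rule covers the Day 7 dose. The Day 8 trough therefore follows a dose given under a different condition from those behind the Day 3-7 troughs. The SAP does not give this as its reason for omitting Day 8. It is a caveat, not a bar.

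**Conclusion.** The concern holds as a nearly free improvement with a small effect. The model leaves out a collected sample that is the Ctau of the interval named in its conclusion, and keeps a Day 1 sample that cannot contribute. The loss is one of precision: a 21% reduction in slope SE forgone on Days 2-7, with almost no change in the verdict at the predicted half-life (60% against 63% of intervals covering zero at an assumed SD of 0.20). The present test is not invalid on this account.

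The benefit is larger within a late-trough set, and only if elimination is slower than predicted. The 9.27 h is an allometric prediction made before any human data. The residual SD and the longer half-lives are assumptions.

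The rule that the slope interval must include one matters more than the omitted sample and would survive its inclusion.

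**What to change.** - Define the analysed Ctau in SAP 6.3.12.5 as a pre-specified set of late troughs that includes the 24-hour sample after the last dose, coded as Day 8. Pre-dose Days 4-7 plus Day 8 is one example.
- Drop the Day 1 pre-dose sample.
- Align the rest of the paragraph, including the phrase that places the analysis before Day 7, and the WHERE statement.
- In the same edit, correct the decision rule so that the confidence interval for the log-scale slope is compared with zero. Without this the change of samples has no effect on the conclusion.

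**Cost.** A few lines of SAP text and one line of code. The sample is already scheduled for collection and assay.

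**Downside.** A late set has fewer points. The slope SE for Days 4-8 is √(17.5/10) = 1.32 times that for Days 2-7. If the half-life were really 48 h with SD 0.30, the interval would still cover zero in 33% of simulations, where Days 2-7 almost never would. Days 2-7 buy that sensitivity by also rejecting a plateau in about 99% of simulations at 24 h, when the Day 7 trough is already 98% of steady state. The slope and its interval should therefore be reported alongside the verdict, with a note on the food-rule difference behind the Day 8 value.

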C_{max_D}	Maximum observed concentration divided by dose

*Parent drug only

This Table is applicable for Day7 of Multiple ascending dose (Part B).

All urine voided will be collected in the following intervals: pre-dose and 0-24 hours post-dose. Urine samples will be used for qualitative analysis of KM-819 and possible metabolic profiling, if appropriate, and will be reported separately. For cerebrospinal fluid (CSF) PK, the concentration of KM-819 will be listed and no other PK parameters will be calculated as there will be only one sample from each subject.

PAREXEL International
Statistical Analysis Plan

6.1.3.1 *Pharmacokinetic Parameter Calculation Methods*

PK parameters will be calculated by non-compartmental analysis methods from the concentration-time data using WinNonlin (WNL) Professional (Version 6.3 or higher) following these guidelines:

- Actual sampling times relative to dosing rather than nominal times will be used in the calculation of all derived PK parameters.
- There will be no imputation of missing data.
- Any subjects with more than one observed concentration data will be included in the PK analysis set provided that at least C_{max} and $AUC_{(0-t)}$ can be reliably calculated .
- If one or more non-quantifiable (NQ) values occur in a profile before the first measurable concentration, they will be assigned a value of zero concentration. If a single NQ value occurs between measurable concentrations in a profile, the NQ should generally be omitted (set to missing) in the derivation of pharmacokinetic parameters, statistical analysis, and the individual subject plots. If two or more NQ values occur in succession between measurable concentrations, the profile will be deemed to have terminated at the last measurable concentration prior to these NQs. For the purpose of individual subject plots, these NQs will be set to 0, and the subsequent measurable concentrations will be retained. For the derivation of pharmacokinetic parameters, these NQs and any subsequent measurable concentrations will be omitted (set to missing).
- PK parameters following single and repeat dose will be estimated according to the following guidelines:
 - C_{max} will be obtained directly from the concentration-time data.
 - t_{max} is the time at which C_{max} is observed.
 - λ_z will be estimated at terminal phase by linear regression after log-transformation of the concentrations:

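### The SAP's steady-state rule compares a log-scale trough slope with one instead of zero, so flat troughs would be reported as steady state not confirmed

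*SAP*

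**What the plan says.** SAP 6.3.12.5 (Steady State Assessment, Part B only) log-e transforms the trough concentrations and fits a mixed model by dose, with day as a continuous covariate and subject as a random effect. The quantity to be judged is "The coefficient of the slope of the day effect on the log-e scale for each treatment dose", with a 90% confidence interval. The decision rule is "If the 90% limits for the slope is including one then steady-state is statistically confirmed".

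The example PROC MIXED code has the statement "model logCtau = Day/cl alpha=0.1 solution", which prints limits for the raw Day coefficient. No later step exponentiates them.

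On the days to be used, one sentence says that the analysis of trough "levels will be performed before Day 7, after a log-e transformation of the data". The next says "Only pre-dose concentration on days 1-7 for the 7 day analysis will be included in the analysis", and the code has "where (Day in (1,2,3,4,5,6,7".

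The preceding section, SAP 6.3.12.4 (Time Invariance), does ask in words for a back-transformed quantity: "calculating the ratio of the geometric least square means". Protocol 8.7 contains no steady-state rule and leaves further detail to the SAP, so nothing in the protocol overrides SAP 6.3.12.5.

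**The concern.** The rule pairs a slope on one scale with the no-change value of another. If troughs do not change from day to day, the log-scale slope is 0 and its exponential is 1. Asking the untransformed slope's interval to contain 1 asks for evidence of e-fold daily accumulation, which is the opposite of steady state.

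A programmer who follows the text would report that steady state was not confirmed at any dose, even with perfectly flat troughs. A team that notices the problem at reporting would have to change a pre-specified criterion after seeing the data.

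There is a related defect. The text and code include the Day 1 pre-dose sample, which Protocol Table 7-2 (footnote 10) places before the first dose. That value contains no drug, so it says nothing about steady state and has no usable logarithm.

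**Working it through.** **1. The no-change value.** The SAP's model is ln(C_trough) = a + b × Day + subject effect.
- Constant troughs: b = 0, exp(b) = 1.
- b = 1: troughs multiply by e^1 = 2.72 per day, and by e^5 = 148 from Day 2 to Day 7.

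The SAP's reference value of one therefore cannot be reproduced for the slope it defines. It is correct only for exp(b).

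**2. Days that can enter the fit.** Day 1 pre-dose precedes any drug. For parameter derivation, SAP 6.1.3.1 says of unquantifiable values "before the first measurable concentration, they will be assigned a value of zero concentration"; SAP 6.3.12.2 also substitutes zero in descriptive statistics. Neither names this model, but zero is the only substitution the SAP offers. Since ln(0) is undefined, the record drops out and Days 2–7 remain.

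**3. Width of the interval.** In a balanced random-intercept model the 90% half-width is t(0.95, df) × σ / √(n × Sxx), with df = nT − n − 1 and σ = √ln(1 + CV²). For Days 2–7, T = 6 and Sxx = 17.5 per subject. There are n = 6 active subjects per cohort (SAP section 5); n = 12 applies if the code's BY dose statement merges the young and elderly 200 mg cohorts. The within-subject CV is not in the documents and is assumed.

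| CV | σ | half-width, n = 6 (df 29) | half-width, n = 12 (df 59) |
|---|---|---|---|
| 10% | 0.100 | 0.017 | 0.012 |
| 30% | 0.294 | 0.049 | 0.034 |
| 50% | 0.472 | 0.078 | 0.055 |
| 100% | 0.833 | 0.138 | 0.096 |

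An interval centred on 0 would reach 1 at n = 6 only if σ were about 6.0.

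**4. Flat troughs** (20,000 simulated cohorts per setting, CV 15% to 100%, n = 6 and 12).
- Days 2–7: interval includes 1 in 0%, includes 0 in 89.7% to 90.2%; largest upper limit 0.485 (n = 6) and 0.323 (n = 12).
- Days 2–6 (Day 7 excluded): includes 1 in 0%, includes 0 in 89.6% to 90.4%; largest upper limit 0.615 and 0.434.

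One REML fit to simulated flat troughs, as illustration: slope 0.016, 90% CI −0.040 to 0.072, which excludes 1 and includes 0. Exponentiated limits: 0.961 to 1.074, which include 1.

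**5. Rising troughs.** The trough fraction at pre-dose Day d is 1 − exp(−k × 24 × (d − 1)). With assumed half-lives of 6 to 48 h, CV 15% to 100%, and n = 6 or 12, the interval includes 1 in 0% of cohorts in every setting. The largest upper limits were 0.677 (Days 2–7) and 0.941 (Days 2–6). Even with no elimination at all, so that troughs grow in proportion to the number of doses, the least-squares slope of ln(1…6) on Days 2–7 is 0.343, and of ln(1…5) on Days 2–6 it is 0.391. Only troughs rising e-fold daily satisfy the written rule in about 90% of cohorts.

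**6. Sensitivity to Day 1.** Suppose a small non-zero Day 1 value were used instead, which the SAP does not specify. With flat Days 2–7, n = 6 and CV 30%:

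| Day 1 as fraction of trough | slope, Days 1–7 | interval includes 1 | interval includes 0 |
|---|---|---|---|
| 0.01 | 0.49 | 0% | 0% |
| 0.001 | 0.74 | 75% | 0% |
| 0.0001 | 0.99 | 100% | 0% |

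The verdict would then depend on an arbitrary substituted value.

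**The case against.** The best defence is that an exponentiated slope was intended, so that only a sentence is missing. That is quite possible. The example code in SAP 6.3.12.4 does not back-transform either, so absence from the code proves little. But 6.3.12.4 states the ratio scale in its text, whereas 6.3.12.5 names the log-e scale and then applies one to it. The wording needs correcting on either view.

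Several limiting points stand:
- The evidence would not be lost. The interval for the slope is to be calculated, and SAP section 11 lists raw SAS output for Table 14.2.6 as Appendix 16.1.9.4, so a reader could compare the printed limits with zero.
- If Day 1 drops out as an undefined logarithm, the fit is already the Days 2–7 fit, and deleting Day 1 mainly removes ambiguity. The 0% result for flat troughs does depend on that reading, as step 6 shows.
- The Day 7 sample is itself pre-dose, so the two descriptions of the day range can be read as agreeing. This is loose wording more than a firm contradiction.
- The n = 12 case is not settled: SAP section 2 leaves the elderly Part B dose to the Investigator and Sponsor in its text but shows 200 mg in its table. The result has the same direction at n = 6.
- Steady state is not a listed protocol PK endpoint, and trough summaries and accumulation ratios are reported anyway.

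These points limit the consequence; none makes one the right reference for a log-scale slope.

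**Conclusion.** The concern holds, with high confidence. As written, the rule uses the wrong reference value: zero is no change on the log-e scale. With Day 1 dropped and any plausible within-subject variability (CV of 15% to 100% was assumed), it would not confirm steady state for flat troughs and would return the same answer for troughs still accumulating. Comparison with zero gives the expected 90% for flat troughs.

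The effect is limited to the verdict attached to Table 14.2.6. The estimates are unaffected, no safety, escalation or other PK analysis uses the verdict, and PK is a secondary objective. It should be fixed, but it does not threaten the study's main conclusions.

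**What to change.** In SAP 6.3.12.5:
1. Change the reference value from one to zero, or state that the slope and its 90% limits are exponentiated and then compared with one.
2. Remove Day 1 from the text and from the WHERE statement.
3. State the day range once, making clear whether the Day 7 pre-dose sample is included.
4. Show the slope and its 90% interval beside the verdict in Table 14.2.6 itself, and say that an interval including zero means only that no trend was detected.

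The cost is a few words and one line of code, with no new data. If the database is already locked, the SAP's own provision for a SAP Addendum covers the change.

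Point 4 matters because the corrected rule is still a trend test whose result depends on sample size. From Protocol 5.3, k = 2.93 / 39.2 = 0.0747 per hour (half-life 9.27 h), so the Day 2 trough is 1 − exp(−0.0747 × 24) = 83.4% of steady state. At an assumed CV of 20% on Days 2–7, the interval would include 0 in 60% of cohorts with n = 6 but 36% with n = 12, for the same underlying troughs.
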